3.1.2. Focus groups

All focus group participants will initially complete a brief survey of demographic information over the phone or through REDCap (Addendum 3 [PWH], Addendum 4, [providers]). The study team will use a focus group guide that addresses key constructs of the Tailored Implementation of Chronic Diseases (TICD) checklist, an implementation science framework that identifies potential barriers or facilitators of healthcare professional practice and intervention delivery.³⁰ Between 3-5 focus groups of 5-10 patients will be conducted and 10 clinicians will partake in one-on-one interviews, each lasting approximately 1-1.5 hours. Patient focus group size may be reduced in early recruitment or to accommodate participants. The facilitator ([name]) will then go through a widely used decision aid to guide screening, shouldscreen.com (University of Michigan) which includes an estimate of personalized 6-year risk of lung cancer³¹. In provider interviews, two tools to measure competing risks, one to summarize comorbidity (the age-adjusted CCI) and the other to estimate 5-year mortality specifically in PWH (the VACS 2.0

Index), will be introduced alongside a mock tool to aid in shared decision making (Addendum 16).^{32,33} The facilitator will lead discussion of barriers and facilitators across TICD constructs of: 1) tailoring SDM to PWH, and 2) utilizing the measures of competing risk. For example, key TICD constructs for tailoring SDM include determining **patient needs** and **preferences**, and provider assessments of **feasibility** and **attitudes towards the guidelines**. When considering incorporating measures of competing risk, key constructs include the **cultural appropriateness of the recommendation** for both PWH and their providers as well as provider assessments of **consistency with other guidelines** and **relative strength of supporters and opponents**. Interviews with providers will follow patient focus groups and incorporate resultant themes in the discussion. The focus group and interview guide is addended here (Addendum 5.1 and 5.2). These guides will be adapted throughout Aim 1 to improve clarity and receive greater response by patients and providers.

3.1.3. Sample Size

Thematic saturation, the point at which no further theme are generated from subsequent groups, can often be achieved with 3-6 focus groups.³⁴ As we are conducting focus groups/interviews with providers and patients separately, we will allow up to 8 focus groups and 10 interviews, and will use iterative analysis to determine saturation.

3.1.4. Data Collection and Analysis

All focus groups will be recorded and transcribed. We will use a framework analysis approach which combines inductive and deductive methods to generate themes and map them onto an implementation framework; in this case we will map themes onto the constructs of the Tailored Implementation of Chronic Diseases (TICD) checklist.^{30,35} Results will be entirely qualitative and key quotes and field notes will be used as evidence in analysis. Initial focus groups and interviews will be reviewed and coded individually by members of the analytic team ([name], [name], [name] and others as designated), who will then compare coding to reach consensus on a codebook to use in analysis of subsequent focus groups. Codes will then be analyzed through a constant comparison method to determine key themes, again using a framework approach of thematic analysis to map themes onto the specific constructs (such as “patient needs” or “guideline appropriateness”) of the TICD checklist. We will analyze all focus groups in real time to make iterative changes to the focus group guide based on feedback and refining potential methods of SDM.

3.1.5. Reimbursement

All patient participants will be provided with \$40 for participation in the study and if in-person, parking reimbursement. Providers will receive a \$10 gift card for completing the interview.

3.2. Aim 2

3.2.1. Recruitment, enrollment and consent

We will utilize the UW HIV Cohort registry, a subset of the HOPE research cohort who indicated interest in future contact, and provider referrals (see Addendum 17) to identify potentially eligible participants based on age and smoking status. The study coordinator will contact individuals to confirm their eligibility for LCS including assessment of smoking pack-years. Participants who confirm that they are interested in the study will complete verbal consent for a limited chart review to inform risk factors in the shared decision-making tool. This includes age, gender, BMI,

and most recent CD4 count, HIV RNA level, hepatitis C status, eGFR, AST, ALT, platelets, WBC count, hemoglobin and albumin. Individuals eligible for LCS will have a study and SDM visit scheduled, at which time informed consent will be obtained by the coordinator. Research coordinator (RC) will contact potential participants and confirm eligibility. An initial telephone script (Addendum 6) will be used to contact and briefly explain the study. In-person written consent (Addendum 7) will be used at the time of the patient visit. RC will also confirm insurance-coverage eligibility for participant at no cost to the participant through UW radiology scheduling partner.

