2.1. Aims

Aim 1. Conduct a formative evaluation using qualitative methods to guide adaption and implementation of shared decision making (SDM) for LCS tailored to PWH incorporating lung cancer risk as well as HIV severity, comorbidity and life expectancy.

H1. Key themes will emerge from focus groups and interviews with PWH and providers that will help structure a SDM process for PWH and determine how best to incorporate measures of HIV severity, comorbidity and life expectancy, such as the Veterans Affairs Aging Cohort Study and Charlson Comorbidity risk indices.

Aim 2. Pilot and evaluate tailored SDM using mixed-methods to assess the impact on patient knowledge and decisional conflict, as well as intervention acceptability, appropriateness and fidelity.

H2. Tailored SDM will result in improvements in patient knowledge and result in low levels of decisional conflict. Surveys of patients and interviews of patients and stakeholders will be utilized to inform and subsequently iterate the intervention with regards to acceptability, appropriateness and fidelity.

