2.4. Study Population

2.4.1. Inclusion Criteria

Aim 1. We will recruit participants from two groups: PWH enrolled in the local UW HIV cohort and primary providers at Madison Clinic and other Seattle-based clinics serving PWH. Using proposed USPSTF guidelines, participants enrolled in the registry who are current or former smokers, ≥ 50 years old, and report ≥ 20 pack-years smoking history (n=165) will be eligible for recruitment. A purposive sample will be recruited, making every effort to include patients of diverse race/ethnicity, sex, income, and spanning the eligible age range for LCS. We will pay particular attention to recruiting women as well as men. Clinicians (medical doctors, physicians assistants, and nurse practitioners) who provide primary care for PWH (n=48) will be eligible.

Aim 2:

PWH who are eligible for LCS based on current USPSTF criteria^[SMA1]. Plan to enroll approximately 50% who have never had a lung cancer screening exam, and 50% who are overdue (~12 months) for lung cancer screening exam.

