2.4.2. Exclusion Criteria

Those found to be ineligible for LCS on coordinator review; or who are non-English speaking or have cognitive dysfunction that would prevent participation in SDM.

3. Study Procedures

3.1. Aim 1

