3.1.1. Recruitment, enrollment and consent

PWH who are recruited for focus groups will be identified through the research registry (in which they have consent for contact for any future studies). Participants will be recruited from the registry who meet the following criteria: current or former smokers, ≥ 50 years old, and report ≥ 20 pack-years smoking history (n=165). The research coordinator (RC) will contact potential participants and confirm eligibility. An initial telephone script (Addendum 1) will be used to contact and briefly explain the study. Verbal consent (Addendum 2.1, Addendum 2.2) will be used prior to the focus groups. Participant clinicians will be recruited by Madison clinic provider [name] with the assistance of the RC. Participant clinicians will also complete an electronic consent prior to the interviews (Addendum 2.3). An informational flyer will also be posted at UW Madison Clinic (Addendum 15.1) throughout Aim 1 enrollment.

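### Does Aim 2 need to flag people who attended an Aim 1 focus group and show its results without them?

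*Combined protocol and SAP*

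**What the plan says.** Section 3.1.1 gives the source of Aim 1 patients: "PWH who are recruited for focus groups will be identified through the research registry". The eligible pool there is 165. In the focus groups (section 3.1.2) the facilitator "will then go through a widely used decision aid to guide screening, shouldscreen.com". The competing-risk measures and the mock decision tool are placed elsewhere: "In provider interviews, two tools to measure competing risks" are introduced there together with that mock tool.

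Aim 2 recruitment (section 3.2.1) reads: "We will utilize the UW HIV Cohort registry, a subset of the HOPE research cohort who indicated interest in future contact, and provider referrals". Inclusion for Aim 2 (section 2.4.1) is "PWH who are eligible for LCS based on current USPSTF criteria", with about half never screened and about half overdue. The exclusions in section 2.4.2 are "Those found to be ineligible for LCS on coordinator review; or who are non-English speaking or have cognitive dysfunction that would prevent participation in SDM". Earlier Aim 1 participation is not mentioned in any of these places, in the survey content of section 3.2.2, or in the analysis of section 3.2.6.

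The hypothesis for Aim 2 (section 2.1) is "Tailored SDM will result in improvements in patient knowledge and result in low levels of decisional conflict". Knowledge is measured before and after the visit. Decisional conflict, acceptability and appropriateness are measured once, after it.

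**The concern.** A person who has spent 1 to 1.5 hours in a group on lung cancer screening, including a walk-through of a decision aid, is not new to the subject. Two things could follow.

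- **Knowledge.** The pre-visit score could already be raised, so the measured improvement would be too small and its cause unlabelled.
- **Post-visit scores.** Decisional conflict, acceptability and appropriateness have no baseline and no comparator, so an effect of earlier exposure could not be seen. The nurse practitioner also uses language developed in Aim 1, so some participants might be rating material that their own group helped to shape.

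The pilot is meant to support a later multicentre trial, whose patients would mostly not have attended these groups. A flag and a with/without table therefore look like a cheap safeguard.

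**Working it through.** **The plan's own figure.** Section 3.2.5 cites an earlier study in which understanding of harms rose from 69% to 93% in 45 patients, p=0.002. Taking 31/45 = 68.9% and 42/45 = 93.3%, the net change is 11 patients. With 12 improving and 1 worsening, uncorrected McNemar gives (12−1)²/13 = 9.31, p=0.0023. The p-value is plausible for a paired test, though the discordant counts are not stated. The gain is 93 − 69 = 24 points, for one knowledge item rather than the whole scale.

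**Size of the overlap.** Inputs: pool 165 (sections 2.4.1 and 3.1.1); Aim 1 patients 3×5 = 15 to 5×10 = 50 (section 3.1.2, which also allows smaller groups); Aim 2 target 50 (section 3.2.5). Section 3.1.3 says "we will allow up to 8 focus groups and 10 interviews", but that allowance is introduced for providers and patients taken separately, so the specific patient plan of 3 to 5 groups is used. Expected overlap = (Aim 2 patients drawn from the pool) × (Aim 1 patients) / 165, assuming a random draw.

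| Drawn from the 165 | 15 in Aim 1 | 50 in Aim 1 |
|---|---|---|
| All 50 | 50×15/165 = 4.5 (9.1% of 50) | 50×50/165 = 15.2 (30.3%) |
| 25 of 50 | 25×15/165 = 2.3 (4.5%) | 25×50/165 = 7.6 (15.2%) |

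Under this assumption the chance of at least one overlapping person is 0.92 or more. The half split is also an assumption; the protocol gives no share per route.

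**Effect on the knowledge gain.** Let f be the overlapping share and c the fraction of the gain already present at baseline, with the same post-visit level. Observed gain = 24 × (1 − f×c).

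| | c = 0.5 | c = 1 |
|---|---|---|
| All 50 from the pool | 22.9 to 20.4 | 21.8 to 16.7 |
| 25 from the pool | 23.5 to 22.2 | 22.9 to 20.4 |

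Every value lies below 24: the error is towards too small a gain. Section 2.3.1 puts Aim 1 in months 1–10 and Aim 2 in months 11–24, so exposure would lie between 11−10 = 1 and 24−1 = 23 months before the knowledge test. Full carry-over is an outer bound.

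**What removing Aim 1 patients would buy.** The worst planned case is 15 overlapping with full carry-over. Assume 2% worsen and use an exact two-sided McNemar test at 0.05. Power is then 0.71 keeping all 50 and 0.76 using the other 35, against 0.93 with no overlap. Exclusion recovers little.

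**What the table could separate.** It would drop about 2 to 15 people, chosen purposively and willing to volunteer twice, so any difference mixes exposure with selection. It would keep the overdue half of Aim 2 (0.5×50 = 25). Section 2.4.1 lists them apart from the never screened, and section 1.2.5 notes that shared decision making is mandated for this screening. Earlier screening discussions may thus be a larger source of prior exposure than Aim 1.

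**The case for a change.** The best case for a change rests on the outcomes measured only after the visit. For these there is no baseline to reveal carry-over, the direction is not obviously conservative, and the second half of the Aim 2 hypothesis depends on one of them. Interviewees are also chosen partly for their spread on the acceptability and appropriateness scores, so overlap could reach the qualitative sample. The remedy is one data field and one table, and eligibility and the main analysis would stay as they are.

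Much of this stands as description. The registry is shared, the protocol text is silent, and under a random draw some overlap would be likely. But the documents support no figure for an effect on decisional conflict or the two scales. Section 3.2.6 only summarises them, without a cut-off or test, so no planned conclusion could reverse. Nothing shows that patients saw the tool they would rate in Aim 2, because the mock tool belongs to the provider interviews. The Aim 2 telephone script and survey are addenda outside the public text and may already ask about earlier participation. What survives is a reporting courtesy: state how many Aim 2 participants had been in Aim 1. The coordinator contacts patients in both aims, and section 4.3.1 describes study IDs with a linkage sheet holding medical record numbers, so the count should be obtainable without a new procedure.

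**Conclusion.** The silence is real but calls for no change to the plan. Expected overlap is about 5 to 15 of 50 if all of Aim 2 came from the Aim 1 pool, and about 2 to 8 if half did; the documents do not say that anyone will take part in both. On knowledge, a 24-point gain would show as 16.7 to 23.5 points under half to full carry-over, an understatement that cannot create a false improvement. On the single-measurement outcomes no effect size can be given and no decision rule is at risk. A with/without table could be added for description, but it would not isolate the effect of earlier study exposure.

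These figures rest on random sampling, which neither aim uses, on an assumed route split and assumed carry-over, and on the pool of 165. That pool was counted under the proposed screening criteria, whereas Aim 2 applies the current ones. They show scale only. In a single-arm feasibility study without a power calculation, this is a gap that analysts can fill when they describe the sample.

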3.2.2. Shared Decision Making visit

The coordinator will administer a pre-SDM survey that includes participant demographics, participant-reported risk factors, tobacco history, an assessment of LCS knowledge (the LKS) used in our prior study³⁶ and minimalist/maximalist approach to healthcare⁴⁰ (Addendum 8.1). Participants will then meet with the LCS nurse practitioner (NP), who will provide the SDM intervention and will supplement the discussion using language regarding comorbidity and life expectancy developed in Aim 1 to frame decisions; they will come to a mutual decision on whether to move forward with the screening process. To inform the tailored discussion, comorbidity burden and life expectancy will be estimated for each participant prior to the visit, using data from the UW HIV Information System (UWHIS) and EPIC to generate CCI, LCRAT, LCDRAT and VACS 2.0 Index from electronic-health records data (ICD-10 codes and most recent lab values within 1 year). A HIPAA waiver has been requested for this purpose. Prior to the visit, the participants lung cancer risk will be calculated using the LCRAT and the LCDRAT tools and mortality risk will be calculated using the VACS Index 2.0. The NP will receive an interpretation of these results, based on published literature and our preliminary work to guide discussion. The NP will complete SDM with the patient using the tailored SDM tool (Addendum 19) and guide (Addendum 20). The coordinator will observe the SDM discussions in order to complete an observational checklist assessing fidelity of the intervention (Addendum 9). Participants will then complete a post-SDM survey re-assessing LCS knowledge, resultant decisional conflict using the low literacy decisional conflict scale,³⁷ as well as validated quantitative 4-item scales of acceptability and appropriateness developed by Co-I [name], the Acceptability of Intervention Measure (AIM) and the Intervention Appropriateness Measure (IAM)(Addendum 8.2)³⁸ Participants who go on to LCS will be enrolled in the LCS program and linked to screening by a patient navigator.

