3.2.3. Post-intervention interviews

Approx. 5 weeks post-SDM, 10-15 purposefully selected participants chosen to represent both broad demographics and maximum variation on AIM and IAM scores will be contacted for a 45-minute telephone or HIPAA-approved ZOOM interview to explore factors that might influence intervention acceptability and appropriateness. These will be conducted by the RC. Similar interviews will be conducted with the NP. Interview guides (Addenda 10, 11, 12) will be adapted throughout Aim 2 to better capture participant perspectives. The NP interview will also explore factors that might influence fidelity of intervention delivery. All interviews will be recorded and transcribed. This will have separate consent delivered over the phone by RC (Addendum 13.1 and 13.2).

3.2.4. Review of EHR.

Participants in Aim 2 will provide consent and HIPAA authorization (Addendum 14) for limited review of their medical records at the time of clinical visit. A HIPAA waiver has been requested

for review of EHR prior to clinical visit to determine comorbidity burden and life expectancy measures used in production of a tailored SDM tool. The EHR will be assessed for participants to determine the following information post-SDM visit: data of lung cancer screening scheduling, documentation of patient encounters around lung cancer screening, lung cancer screening results, lung cancer screening follow-up screening, procedures, and patient visits.

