4.4. Informed Consent and HIPAA Authorization

A waiver of documentation of consent has been approved, as of 2/3/2021, for patients and providers in Aim 1. As above, written informed consent will be obtained for each SDM study participant in Aim 2. A HIPAA authorization will be required for these subjects participating in Aim 2 SDM given limited review of the participants EHR. A HIPAA waiver has been requested for limited review of participants EHR, prior to formal consent/HIPAA authorization, specific to creation of tailored SDM tool. A waiver of documentation of consent has been requested for remote delivery of Aim 2 post- interview participants.

5. Safety Management

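### Do the differing descriptions of the pre-visit record review, and the unstated smoking source for the lung cancer risk scores, call for a change to the plan?

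*Combined protocol and SAP*

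**What the plan says.** Four sections of the combined protocol and SAP touch this step.

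- **Section 3.2.1 (Recruitment, enrollment and consent).** The coordinator contacts candidates to "confirm their eligibility for LCS including assessment of smoking pack-years". Those who are interested "will complete verbal consent for a limited chart review to inform risk factors in the shared decision-making tool". The items then named are age, gender and BMI, "and most recent CD4 count, HIV RNA level, hepatitis C status, eGFR, AST, ALT, platelets, WBC count, hemoglobin and albumin".
- **Section 3.2.2 (Shared Decision Making visit).** Comorbidity and life expectancy are to be estimated beforehand, with UWHIS and EPIC as the sources. Staff will "generate CCI, LCRAT, LCDRAT and VACS 2.0 Index from electronic-health records data (ICD-10 codes and most recent lab values within 1 year". The next sentence says that a HIPAA waiver has been requested for this. The section then adds: "Prior to the visit, the participants lung cancer risk will be calculated using the LCRAT and the LCDRAT tools", with VACS 2.0 for mortality risk. Tobacco history is also asked in the survey given at the visit, before the nurse practitioner's discussion.
- **Section 3.2.4 (Review of EHR).** The requested waiver is for "review of EHR prior to clinical visit to determine comorbidity burden and life expectancy measures used in production of a tailored SDM tool".
- **Section 4.4 (Informed Consent and HIPAA Authorization).** The waiver covers limited review "prior to formal consent/HIPAA authorization, specific to creation of tailored SDM tool". On consent documentation, the section reports an approved waiver for Aim 1, and for Aim 2 says: "A waiver of documentation of consent has been requested for remote delivery of Aim 2 post- interview participants". It does not mention the verbal consent of 3.2.1.

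**The concern.** Read side by side, the sections appear to describe one step in several ways. The list attached to verbal consent has no diagnosis codes, yet the Charlson index (CCI) is to come from the record and ICD-10 codes are one of the two named source types. The waiver's purpose is worded around comorbidity and life expectancy in 3.2.4 but around the whole tool in 4.4, while 3.2.2 describes two of the four scores as lung cancer risk. Section 4.4 is silent on the verbal consent.

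LCRAT and LCDRAT are to be calculated before the visit from record data, and no smoking field is named among those data.

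If these were true conflicts, two things would be at stake. One is privacy, which Section 4.3.1 gives as the main risk: a coordinator might take data outside the permission given. The other is reproducibility: the tool might rest on different smoking inputs for different participants, which would hamper the later multicenter trial foreseen in the introduction.

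**Working it through.** No sample size, power or error-rate figure is involved. The check is a comparison of the text in four parts.

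**1. Data items.** Section 3.2.1 names 3 items (age, gender, BMI) plus 10 (CD4, HIV RNA, hepatitis C status, eGFR, AST, ALT, platelets, WBC, hemoglobin, albumin): 3 + 10 = 13. Diagnosis codes among them: 0. Smoking fields: 0. The list opens with a form of the verb include, so it is not stated to be closed. The bracket in 3.2.2 is a short gloss on data from UWHIS and EPIC. It leaves out age, gender and BMI, but nothing suggests that these are unavailable or barred. The one concrete omission is diagnosis codes in 3.2.1.

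**2. Permission.** Verbal consent and a HIPAA waiver are different instruments and can both apply; Section 1.3 cites 45 CFR 46 and the HIPAA Privacy Rule separately. Sections 3.2.2, 3.2.4 and 4.4 agree that a waiver has been requested for the pre-visit review. In 3.2.2 the sentence on the waiver directly follows the one naming ICD-10 codes, so the permission sought for those codes is stated. Section 4.4 places the waiver before formal consent, which leaves room for an earlier verbal step. What remains is that 4.4 does not list that step.

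**3. Purpose of the waiver.** Section 3.2.2 puts all four scores (CCI, LCRAT, LCDRAT, VACS 2.0) under the heading of comorbidity and life expectancy, then ties the waiver to that purpose. Section 3.2.4 uses the same heading and adds production of the tool. In the protocol's own usage, 3.2.4 can therefore cover 4 of 4 scores, as 4.4 does. The later sentence in 3.2.2 that calls two of them lung cancer risk is looser wording; it does not narrow the waiver. Section 4.3.1 also describes the record review as bearing on lung cancer screening, though that may partly refer to the review after the visit.

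**4. Smoking input.** The documents do not list the inputs of LCRAT or LCDRAT. That they use smoking history is an assumption, though a reasonable one, since Section 1.2.1 attributes the excess lung cancer in this population largely to tobacco. On that assumption the order of events is:

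| Step | Smoking information |
|---|---|
| Identification of candidates (3.2.1) | Smoking status |
| Eligibility contact (3.2.1) | Pack-years |
| Scores calculated before the visit (3.2.2) | Source not stated |
| Survey at the visit (3.2.2) | Tobacco history |

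Pack-years are thus in hand before the scores are due. What is missing is a linking phrase.

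**5. Effect on the analysis.** The outcomes in Section 3.2.6 are knowledge, decisional conflict, acceptability, appropriateness and fidelity. None takes a risk score as an input, and none measures score accuracy.

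**The case for a change.** The strongest case for a change starts from the 13 named items. A list that specific will be read as the scope of what the participant agreed to, and it leaves out one of the two source types named in the next section. The step applies to all of the planned 50 or more participants, and the remedy would be a few words in four sections. Section 4.4 deals with waivers of documentation for Aim 1 and for the Aim 2 interviews, so its silence on the other Aim 2 verbal consent stands out. The survey's tobacco history also comes after the scores are calculated, so an answer that differs from the earlier pack-years has no stated route into the tool.

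The omissions are real, and so is the silence in 4.4. They do not amount to contradiction: no section forbids what another requires. The telephone script, the waiver request and the tool with its guide, where these details would be settled, were not available for this review. Checking the scores against the survey before the discussion would go beyond wording. It would add a step at the visit and perhaps a recalculation, with no gain for any pilot outcome.

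**Conclusion.** The concern does not call for a change. Two small gaps are confirmed: the 3.2.1 list omits the diagnosis codes used in 3.2.2, and no section links the pack-years from the eligibility contact to LCRAT and LCDRAT. A third, minor, is that 4.4 does not mention the verbal consent. These are details that a coordinator working with the waiver and the telephone script would fill sensibly. The supposed conflicts over permission and over the waiver's scope do not survive a reading of 3.2.2 with 3.2.4 and 4.4. The size is nil for sample size, error rates and every stated analysis.

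This rests on three assumptions: that the 3.2.1 list is not meant to be exhaustive, that the unseen waiver request matches its description in 3.2.2, and that LCRAT and LCDRAT use smoking history. If they do not, the smoking point falls away altogether.
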